10.3.3 Data Listings

Data listings will be prepared by treatment group and center for all patients with any abnormal laboratory value at any time-point (including screening, baseline).

TLF Listing: Patients with abnormal laboratory measurements

Page 39 of 51

10.3.4 Urinalysis

Incidence of changes in urinalysis will be summarized by treatment. A summary table with number of patients with change from *Absent* at baseline to *Present* during trial will be summarized.

TLF Table: Incidence of changes from baseline in urinalysis measurements during the trial – Safety Analysis Set

10.4 Vital Signs

10.4.1 Vital Signs

Baseline for all vital signs analyses will be the values obtained at the last assessment prior to the first dose of IMP. Treatment-emergent vital signs data will include tests completed after the first dose of IMP through the time of residual drug effect. End of trial will include the last post-baseline observation during the trial.

10.4.1.1 Summary Statistics

Mean change and mean percentage (%) change from baseline at end of trial will be presented for each vital signs variable. In addition, descriptive statistics, i.e., the number of patients with data, mean (standard deviation), median, minimum, and maximum values, will be presented for observed values and change from baseline at each time-point for each vital signs variable.

TLF Table: Summary of vital signs parameters by visit – Safety Analysis Set

10.4.1.2 Markedly Abnormal Changes

Summary tables will be prepared displaying the number and percentage of patients with normal baseline values who had one or more pre-specified markedly abnormal treatment-emergent value, as defined in Appendix 1.

TLF Table: Incidence of Markedly abnormal vital signs measurements – Safety Analysis Set

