### **7.2.4.2 Vital Signs**

Systolic and diastolic blood pressure (mmHg) and pulse (beats per minute) will be measured after resting for a minimum of 5 minutes in a sitting position at each visit throughout the trial. Assessments of vital signs must be performed prior to dosing if a dosing visit is scheduled.

At Visit 2, the systolic and diastolic blood pressure must not exceed 180 mmHg or 110 mmHg, respectively. If the initial reading exceeds these values, a second reading may be taken two or more hours later; the patient may be included (if all other inclusion criteria are met) in the trial if the second reading demonstrates a systolic blood pressure  $\leq$ 180 mmHg and the diastolic blood pressure is  $\leq$ 110 mmHg. If the blood pressure is brought to 180 mmHg systolic or less and 110 mmHg diastolic or less by antihypertensive treatment, the patient can become eligible.

Vital sign measurements outside normal ranges will be assessed as ‘abnormal, not clinically significant’, or ‘abnormal, clinically significant’ by the Investigator. ‘Abnormal, clinically significant’ measurements at the Screening visit will be recorded as medical history. ‘Abnormal, clinically significant’ changes in vital sign measurements will be reported as adverse events.

The process of evaluating potential CV-related vital signs is described in the CEC Charter in a separate document. Data on suspected CV-related vital signs will be delivered to the CEC Committee before the adjudication of MACE takes place (Sections 7.1.1 and 3.4.1). Potential CV-related vital sign results will be closely followed.

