### **9.8.3 Vital Signs**

Mean change and mean percentage (%) change from baseline at End-of-Trial will be presented for each vital sign variable. Also, the actual values and changes from baseline in vital signs will be tabulated by visit. Incidence of markedly abnormal changes in vital signs values will be summarized and results adjudicated by the CEC Committee as MACE components will be listed.

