Appendix 1 Markedly Abnormal Vital Signs and Electrocardiograms (ECGs)

Table 2 Markedly abnormal Criteria for Vital Signs*

Variable	Criterion Value	Change from Baseline
Systolic blood pressure	$\geq 180 \text{ mmHg}$ $\leq 90 \text{ mmHg}$	Increase of≥20 mmHg Decrease of≥20 mmHg
Dia stolic blood pressure	$\geq 105 \text{ mmHg}$ $\leq 50 \text{ mmHg}$	Increase of≥15 mmHg Decrease of≥15 mmHg
Pulse rate	≥ 120 bpm ≤ 50 bpm	Increase of≥15 bpm Decrease of≥15 bpm
Body weight	None	Increase of≥7% Decrease of≥7%
Body temperature	≥38.3°C	Increase to ≥39.4°C

^{*} To be identified as markedly abnormal, a treatment value must meet the criterion value and also the specified change from baseline.

Table 3 Abnormal Criteria for Quantitative ECG Data

Variable	Baseline	Abnormal Treatment-Emergent Value
ECG heart rate	Normal	≤ 50 bpm and decrease from baseline of ≥ 15 bpm ≥ 120 bpm and increase from baseline of ≥ 15 bpm
Duration of PR interval	Normal	≥ 220 msec
Duration of QRS interval	Normal	≥ 120 msec
Duration of QTc interval	Normal	≥ 450 msec
Duration of QTc interval	Normal	≥ 480 msec
Duration of QTc interval	Normal	≥ 500 msec
Duration of QTc interval	Not applicable	Increase from baseline of≥30 msec
Duration of QTc interval	Not applicable	Increase from baseline of ≥ 60 msec

Page 45 of 51

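### The SAP's incidence table of markedly abnormal vital signs counts only patients with an undefined normal baseline, so it misses events that start from a raised blood pressure

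*SAP*

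**What the plan says.** SAP 10.4.1.2 says the summary table will give the "number and percentage of patients with normal baseline values who had one or more pre-specified markedly abnormal treatment-emergent value", with markedly abnormal defined in Appendix 1.

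The footnote to Appendix 1 Table 2 gives a two-part rule: "To be identified as markedly abnormal, a treatment value must meet the criterion value and also the specified change from baseline". For high systolic pressure this means at least 180 mmHg with a rise of at least 20. For high diastolic pressure it means at least 105 mmHg with a rise of at least 15. The low-side rules are at most 90 mmHg with a fall of at least 20, and at most 50 mmHg with a fall of at least 15. Table 2 has no column for baseline status. Table 3, for ECG data, does have one.

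Protocol 9.8.3 plans the same output without a baseline condition: "Incidence of markedly abnormal changes in vital signs values will be summarized". On who can enter, Protocol 7.2.4.2 says that at Visit 2 "the systolic and diastolic blood pressure must not exceed 180 mmHg or 110 mmHg, respectively". That section refers to normal ranges for vital signs but gives no numbers, and the SAP gives none either. SAP Section 12 names the revised key secondary endpoints and a general reduction of the plan after early termination. It does not name this restriction.

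**The concern.** Change in vital signs is a named safety endpoint, and every patient has pre-existing cardiovascular disease. The table in SAP 10.4.1.2 is the only planned output that gives a rate of Table 2 events. Patients whose baseline pressure is raised but within the entry limit are the ones closest to the high threshold, and the wording takes them out of both numerator and denominator.

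Table 2 does not need that protection. Its change-from-baseline condition already stops a pre-existing high value from being counted as new. With the restriction added, the reported rate answers a narrower question than the protocol's wording suggests. Because normal is undefined, a reader could not say which patients the rate describes. For body weight, where Table 2 lists no criterion value, it is unclear what a normal baseline would be.

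**Working it through.** The plan states no figure to reproduce, and the documents give no baseline blood-pressure distribution. The check is arithmetic on the published thresholds.

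**Inputs.** Criterion value C and required change D come from SAP Appendix 1 Table 2: systolic high 180 and 20, diastolic high 105 and 15, systolic low 90 and 20, diastolic low 50 and 15. The entry limit of 180/110 mmHg comes from Protocol 7.2.4.2. The upper limit of normal, U, is an assumption, so a range is shown.

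**Step 1: does an eligible patient meet Table 2 and go uncounted?** Take a baseline of 165 and a later value of 200.
- Entry: 165 does not exceed 180, so he is eligible on blood pressure.
- Criterion: 200 ≥ 180, met.
- Change: 200 − 165 = 35 ≥ 20, met.
- SAP 10.4.1.2: counted only if 165 is a normal baseline. On an ordinary meaning it is not.

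**Step 2: when does the high-side change condition matter?** From baseline b, the smallest qualifying rise is max(D, C − b). The change condition is the binding one when b > C − D.
- Systolic: 180 − 20 = 160, so it binds only for baselines above 160.
- Diastolic: 105 − 15 = 90, so it binds only for baselines above 90.

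**Step 3: smallest countable rise once baseline must be normal.** Put b = U, in whole mmHg.

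| Measure | Assumed U | max(D, C − U) | Table 2 alone |
|---|---|---|---|
| Systolic | 139 | max(20, 41) = 41 | 20 |
| Systolic | 129 | max(20, 51) = 51 | 20 |
| Systolic | 119 | max(20, 61) = 61 | 20 |
| Diastolic | 89 | max(15, 16) = 16 | 15 |
| Diastolic | 84 | max(15, 21) = 21 | 15 |
| Diastolic | 79 | max(15, 26) = 26 | 15 |

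With normal below 140, the systolic change condition never binds. For diastolic pressure with normal below 90, it also never binds, but the smallest countable rise moves only from 15 to 16.

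**Step 4: low side.** Here the change condition binds when b < C + D.
- Systolic: 90 + 20 = 110.
- Diastolic: 50 + 15 = 65.

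Baselines just below these values can be normal, so the low-side change conditions still do work under the restriction. Redundancy is a high-side result only.

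**Step 5: the most lenient reading.** Suppose normal means only that the baseline does not already meet the Table 2 criterion value. Then every systolic baseline below 180 stays in. Since entry is capped at 180, almost nobody is lost from the high-systolic row.

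**The case against.** The strongest reply is that the loss depends on a definition the documents do not supply. On the reading in Step 5 it is near zero for high systolic pressure. That stands as a limit on size. It does not rescue the text, because Protocol 7.2.4.2 speaks of normal ranges, which does not suggest a cut-off of 180, and an undefined denominator needs fixing on any reading.

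A second reply is that Table 2 defines an abnormal value while 10.4.1.2 defines who is counted, so the two do not contradict each other. Table 3 itself pairs a normal baseline with a threshold and a change for ECG heart rate. The protocol leaves analysis detail to the SAP. This also stands: a reader might infer a conflict with Table 2 or with Protocol 9.8.3, and the documents support only an added, undeclared condition. The difference is that Table 3 states its baseline condition and Table 2 does not.

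A third reply is that large rises would still be visible. SAP 10.4.1.1 gives the minimum and maximum of observed values and of changes at each time-point for the Safety Analysis Set. Clinically significant changes are reported as adverse events (Protocol 7.2.4.2) and tabulated by treatment (SAP 10.2.2). The listing in SAP 10.4.1.3 has no baseline limit. This is correct, so the stronger inference that safety reporting could look clean while large rises occur is not supported. None of those outputs, however, gives the rate of Table 2 events.

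A reader might also infer that hypertensive patients are removed as a class. They are not: selection is on the baseline reading, so a treated patient with a normal reading stays in.

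**Conclusion.** The point holds in limited form. SAP 10.4.1.2 adds a normal-baseline condition that is absent from Protocol 9.8.3 and from Table 2, is not named in SAP Section 12, and is not defined. On an ordinary meaning of normal, patients who meet both written conditions from a raised baseline go uncounted. If normal means below 140 mmHg, the smallest countable systolic rise goes from 20 to more than 40 mmHg.

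It is tempting to say that most high-systolic events disappear from the table. The documents do not support a share. A simulation on assumed inputs illustrates why (baseline mean 130 to 140, SD 15 to 18, truncated at 180; 12 post-baseline readings; regression coefficient 0.6; within-patient SD 12 to 16). It loses 78% to 97% of patients with a high-systolic event if normal is below 140, and 94% to 100% if below 130, while the lenient reading loses almost none. None of those inputs is in the protocol or SAP, so these are not trial figures; only the direction is robust under an ordinary definition.

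The consequence is minor. One descriptive table is affected, in a trial that stopped with 545 patients randomized. The primary analysis, the key secondary tests and type I error control are untouched. It is best treated as a cheap improvement.

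**What to change.** In SAP 10.4.1.2:
- Delete the normal-baseline condition.
- Use as denominator all safety-set patients with a baseline and at least one treatment-emergent value for the variable.
- Keep the two-part Table 2 rule unchanged.
- Show baseline-normal and baseline-abnormal patients as separate rows, with normal defined for each variable, and say how body weight is handled.

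If the sponsor prefers to keep the restriction, define normal and name the restriction in SAP Section 12.

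The cost is one phrase, one programming condition, a definition and an extra table row. No new data are needed. The downside is somewhat higher reported incidences in both arms.

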Appendix 1 Markedly Abnormal Vital Signs and Electrocardiograms (ECGs)

Table 2 Markedly abnormal Criteria for Vital Signs*

Variable	Criterion Value	Change from Baseline
Systolic blood pressure	$\geq 180 \text{ mmHg}$ $\leq 90 \text{ mmHg}$	Increase of≥20 mmHg Decrease of≥20 mmHg
Dia stolic blood pressure	$\geq 105 \text{ mmHg}$ $\leq 50 \text{ mmHg}$	Increase of≥15 mmHg Decrease of≥15 mmHg
Pulse rate	≥ 120 bpm ≤ 50 bpm	Increase of≥15 bpm Decrease of≥15 bpm
Body weight	None	Increase of≥7% Decrease of≥7%
Body temperature	≥38.3°C	Increase to ≥39.4°C

^{*} To be identified as markedly abnormal, a treatment value must meet the criterion value and also the specified change from baseline.

Table 3 Abnormal Criteria for Quantitative ECG Data

Variable	Baseline	Abnormal Treatment-Emergent Value
ECG heart rate	Normal	≤ 50 bpm and decrease from baseline of ≥ 15 bpm ≥ 120 bpm and increase from baseline of ≥ 15 bpm
Duration of PR interval	Normal	≥ 220 msec
Duration of QRS interval	Normal	≥ 120 msec
Duration of QTc interval	Normal	≥ 450 msec
Duration of QTc interval	Normal	≥ 480 msec
Duration of QTc interval	Normal	≥ 500 msec
Duration of QTc interval	Not applicable	Increase from baseline of≥30 msec
Duration of QTc interval	Not applicable	Increase from baseline of ≥ 60 msec

Page 45 of 51

Appendix 2 SMQs for AE Medical History of Special Interest

Table 4 Cardiovascular Events

SMQ	SMQ code
Myocardial infarction	20000047
Ischaemic central nervous system vascular conditions	20000063
Haemorrhagic central nervous system vascular conditions	20000064
Embolic and thrombotic events, arterial	20000082
Other ischaemic heart disease	20000168

Table 5 Diabetes Events

SMQ	SMQ code
Hyperglycaemia/new onset diabetes mellitus	20000041

Page 46 of 51

Appendix 3 ATC codes and MedDRA terms for disease progression

A list of ATC codes for antiandrogens and additional therapies classified as disease progression are defined below. Please note that the list may be non-extensive.

Table 6 ATC Codes for Antiandrogens

Level 5 codes
L02BB01 Flutamide
L02BB02Nilutamide
L02BB03Bicalutamide
L02BB04Enzalutamide
G03HA01 Cyproterone

Table 7 ATC codes for Additional Therapy

Level 5 codes
L01DB07Mitoxantrone
L01CD02Docetaxel
L01XX11 Estramustine
L01CD01 Paclitaxel
L02AA01 Diethylstilbestrol
L02AA02 Polyestradiol phosphate
L02AA03 Ethinylestradiol
L02AA04 Fosfestrol
L02AB01 Megestrol
L02BG01 Aminoglutethimide
L02BX03 Abiraterone
G01AF11 Ketoconazole

Investigators recording of disease progression are marked as a tick-box on the Adverse Event form in the eCRF. The MedDRA terms to be used for radiation and second line treatment are defined below.

Page 47 of 51

Table 8 MedDRA Codes (preferred terms) for Radiation

10006089	Brachytherapy to prostate	PT
10014442	Electron radiation therapy to prostate	PT
10017683	Gamma radiation therapy to prostate	PT
10034955	Photon radiation therapy to prostate	PT
10061544	Radiotherapy to prostate	PT
10048205	X-ray therapy to prostate	PT
10014435	Electron radiation therapy to bone	PT
10017675	Gamma radiation therapy to bone	PT
10034947	Photon radiation therapy to bone	PT
10062089	Radiotherapy to bone	PT
10048197	X-ray therapy to bone	PT

 Table 9
 MedDRA Codes (preferred terms) for Second Line Treatment

10061916	Prostatectomy	PT
10050756	Radical prostatectomy	PT
10038961	Retro-pubic prostatectomy	PT
10042594	Supra pubic prostatectomy	PT
10044445	Transurethral prostatectomy	PT

The following terms are also to be classified as investigators recording of disease progression, in case the investigator did not check the tick-box, but only recorded the AE.

Table 10 MedDRA Codes (preferred terms) for additional classification of investigators recording of disease progression

10010264	Condition a ggravated	PT
10061818	Disea se progression	PT
10061819	Disea se recurrence	PT
10048669	Terminal state	PT
10051398	Malignant neoplasm progression	PT
10027452	Meta stases to bone	PT
10027459	Meta stases to lymph nodes	PT
10027457	Meta stases to liver	PT
10027458	Meta stases to lung	PT
10027463	Meta stases to pleura	PT
10062194	Metastasis	PT

Page 48 of 51

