### 1.3 Benefit / Risk Aspects

Treatment with degarelix or leuprolide is expected to be associated with benefits for the population of prostate cancer patients with concomitant CVD and in whom ADT is indicated, leading to delayed progression of prostate cancer or disease symptoms ([Levine, 2010](#)).

Agonists initially stimulate the pituitary GnRH receptors, resulting in a rapid increase in testosterone levels (surge), which might stimulate prostate cancer cells and delay the onset of ADT ([Klotz, 2014](#); [Carter, 2014](#)). This may lead to an exacerbation of clinical complications such as bladder outlet obstructions, spinal cord compression, and bone pain (clinical flare) in patients with advanced disease. Degarelix competitively binds to the GnRH receptor and promptly blocks testosterone production, resulting in a rapid (one to three days) and sustained suppression of testosterone to castrate levels (serum testosterone level  $\leq 50$  ng/dL), thereby avoiding testosterone surge and flare of clinical symptoms.

Patients initiated with a GnRH receptor agonist regimen are on some occasions treated in combination with an anti-androgen during a limited period to avoid symptomatic flare associated with initial testosterone surge. Therefore, metastatic patients considered by the Investigator as requiring treatment with anti-androgen (e.g. bicalutamide 50 mg once a day) for a maximum period of up to 28 days in addition to leuprolide for symptomatic flare protection can be included and treated according to standard-of-care.

The most common side effects of leuprolide are hot flashes, pain (especially joint pain and back pain), injection site pain and fatigue ([LUPRON Prescribing Information, 2014](#)). Leuprolide may also cause impotence.

The risks of treatment with degarelix are likely to be associated with adverse reactions similar to those associated with other ADTs, such as hot flash/flushes, loss of libido, and impotence ([Carter, 2014](#); [FIRMAGON Prescribing Information, 2015](#)).

Mild, transient elevated values of hepatic transaminases have been observed in healthy volunteers as well as prostate cancer patients treated with degarelix ([Carter, 2014](#); [FIRMAGON Prescribing Information, 2015](#)). The hepatic changes observed to date have been transient increases in transaminases without concomitant increases in bilirubin and with no obvious correlation to dose,

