#### **4.3 Restrictions**

##### **4.3.1 Prior and Concomitant Therapies**

Patients must be treatment-naïve with regard to ADT at time of randomization, except for neoadjuvant/adjuvant ADT given in combination with prostatectomy or radiotherapy with curative intent. This treatment should have been terminated at least 12 months prior to randomization.

Concomitant treatment with anti-androgens (e.g. bicalutamide 50 mg once a day) for a maximum period of up to 28 days is allowed in metastatic patients requiring initial symptomatic flare protection at the discretion of the Investigator. Other hormonal management of prostate cancer is not allowed prior to or during the trial (Section 4.1). However, if a patient develops signs of disease progression, e.g. increased clinical signs and symptoms or rising PSA, additional secondary therapy can be added at the discretion of the Investigator to treat the prostate cancer. Patients on secondary treatments will be handled as described in Section 4.3.2.

The Investigator will be encouraged to treat patients for their pre-existing CVD and any CVD that may be diagnosed during the trial according to standard-of-care. Other medication, which is considered necessary for the patient's safety and well-being, may be given at the discretion of the Investigator.

Details of all concomitant medications, and other therapies including surgical procedures, e.g. revascularizations including the main reason for their prescription must be recorded in the medical source data and the eCRF for all eligible patients at the Screening visit. This information should include name of the drug, route of administration, indication, and duration of treatment. It has to be clearly stated if the medication is given to treat progression of the prostate cancer. Any changes (including new therapies) must be recorded at each subsequent trial visit.

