### **9.6.3.7 Time from Randomization to Failure in Progression-Free Survival**

Progression-free survival is a composite endpoint consisting of the following conditions:

- Radiographic disease progression defined as one or more new metastatic skeletal lesions observed on bone scan; one or more new metastatic extra-skeletal lesions at least 1.5 cm in greatest dimension visible on CT or MRI scan as confirmed by the Investigator.
- Introduction of additional therapy related to prostate cancer treatment including radiation, anti-androgens (except for initial flare protection) and second-line treatment.

- PSA failure defined as an increase in serum PSA of 50%, and at least 5 ng/mL, compared to nadir, measured on two consecutive occasions at least 2 weeks apart.
- Death.

Time to PFS failure is therefore defined as the time, measured in days, from randomization to the first occurrence of one of the above composite endpoint criteria. Time to PFS failure will be analyzed using the Kaplan-Meier estimator of the survival function and the log-rank test of the null hypothesis of equal hazard functions. The p-value of the two-sided log-rank test with significance level of 5% will be presented along with plots of the estimated survival functions for the two treatment groups.

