9.3.6 Time from Randomization to Failure in Progression-Free Survival

Progression-free survival (PFS) is a composite endpoint consisting of the following conditions:

- Death
- Radiographic disease progression defined as one or more new metastatic skeletal lesions observed on bone scan; one or more new metastatic extra-skeletal lesions at least 1.5 cm in greatest dimension visible on computed tomography or magnetic resonance imaging scan as confirmed by the Investigator.
- Introduction of additional therapy related to prostate cancer treatment including radiation, anti-androgens and second-line treatment. (ATC and MedDRA codes for disease progression are included in Appendix 3)
- PSA failure defined as the time from randomization to the second occasion (must be at least two weeks apart from the first and correspond to consecutive measurements) in which the PSA value fulfills the following criteria:
 - I. An absolute increase of ≥ 5 ng/ml above nadir and
 - II. An increase of > 50 % of nadir

Time to PFS failure is therefore defined as the time, measured in days, from randomization to the first occurrence of one of the above composite endpoint criteria. Patients discontinuing from treatment/withdrawn from the study will be censored at the time of discontinuation/withdrawal. Time to PFS failure will be analyzed using the Kaplan-Meier estimator of the survival function, the Cox regression model for the hazard rate and the log-rank test of the null hypothesis of equal hazard functions, stratified by age group and region. The p-value of the two-sided stratified log-rank test with significance level of 5% will be presented along with plots of the estimated survival functions for the two treatment groups, stratified by age group and region. The estimated hazard ratio and the associated 95% confidence interval and p-value comparing the treatment with Degarelix to Leuprolide will also be presented.

TLF Table: Secondary Endpoint: Time to PFS Failure - FAS

TLF Figure: Survivor Function for Time to PFS Failure - FAS

Page 30 of 51

9.3.7 Testosterone levels at day 28, 168 and 336 in patients treated with degarelix and leuprolide

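### Applied as written, SAP Appendix 3 Table 9 scores every transurethral prostatectomy as second-line cancer treatment, which is wider than the PFS definition it implements

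*SAP*

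**What the plan says.** The PFS component at issue is worded in SAP 9.3.6 as "Introduction of additional therapy related to prostate cancer treatment including radiation, anti-androgens and second-line treatment". Protocol 9.6.3.7 carries the same restriction: "Introduction of additional therapy related to prostate cancer treatment including radiation, anti-androgens (except for initial flare protection) and second-line treatment". The protocol gives no code list. The SAP does, by reference: "ATC and MedDRA codes for disease progression are included in Appendix 3".

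Appendix 3 opens by saying that the antiandrogens and "additional therapies classified as disease progression are defined below". Before Tables 8 and 9 it says: "The MedDRA terms to be used for radiation and second line treatment are defined below". Table 9 then defines second-line treatment by five preferred terms, all of them prostatectomies. The last is "Transurethral prostatectomy" (10044445). Neither the table nor the text around it states a condition on indication, relatedness to cancer, or case review.

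**The concern.** The endpoint definition restricts the event by purpose. The code list identifies it by procedure alone. The two agree only if every coded procedure is done for prostate cancer.

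That is doubtful for transurethral prostatectomy. The documents do not discuss the operation, but it is general clinical knowledge that it is also done to relieve urinary obstruction, including obstruction not caused by tumour. Protocol 7.2.1.3 names urinary obstruction as the most common symptom of prostate cancer, and the trial measures urinary symptoms through IPSS, a separate secondary endpoint. A derivation that follows Table 9 literally would therefore let some symptom surgery enter PFS as progression.

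At stake are the PFS event count, the hazard ratio and the log-rank p-value planned in SAP 9.3.6. The sensitivity analyses in SAP 9.2.2 concern the primary endpoint, so no planned analysis would show whether PFS depends on this code.

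**Working it through.** **1. Definition against implementation**

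| Place | What makes a procedure count |
|---|---|
| Protocol 9.6.3.7 | Additional therapy, related to prostate cancer treatment |
| SAP 9.3.6 | Same restriction, with codes taken from Appendix 3 |
| SAP Appendix 3, Table 9 | The preferred term alone |

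No sentence in SAP 9.3.6 or Appendix 3 says how the restriction is applied to a coded record. A patient with transurethral prostatectomy for non-cancer obstruction fails the test in the first two rows and passes the test in the third.

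**2. Is the reason for surgery recorded?**

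Protocol 4.3.1 says that details of concomitant medications and "other therapies including surgical procedures, e.g. revascularizations including the main reason for their prescription must be recorded". That sentence is tied to the Screening visit. For later visits the section asks for changes, including new therapies, without repeating the reason. Two other places help. Protocol 8.1 treats the reason for a surgical procedure as an adverse event, and 8.2.2 lists relation to prostate cancer progression among the items logged for each event. A filter is therefore feasible, although the SAP does not use these fields for Table 9 procedures and some reasons may be unclear.

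**3. Size, as an illustration only**

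The documents give no PFS event rate, PFS power or procedure rate, so there is no plan figure to reproduce. The only documentary input is 545 randomized patients (SAP section 3). The size of the FAS is not stated. Assumed: q = 1-3% have a non-cancer transurethral prostatectomy, and p = 10-30% fail PFS for another reason.

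- Operations: 545 × 0.01 = 5.5; 545 × 0.03 = 16.4.
- Other failures: 545 × 0.10 = 54.5; 545 × 0.30 = 163.5.
- Share of counted failures, lowest pairing: 5.5/(163.5 + 5.5) = 3%.
- Share, highest pairing: 16.4/(54.5 + 16.4) = 23%.

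These are upper limits for each pairing, because not every operation adds a failure. A patient who has already failed adds none. One who would fail later only has his date moved. One operated on after stopping treatment is censored under SAP 9.3.6. If operations are independent of other failures, the net addition is 545 × (1 − p) × q:

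- 545 × 0.70 × 0.01 = 3.8, a share of 3.8/(163.5 + 3.8) = 2%.
- 545 × 0.90 × 0.03 = 14.7, a share of 14.7/(54.5 + 14.7) = 21%.

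**4. Effect on the hazard ratio if rates are equal**

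Let h = −ln(1 − p) be the hazard of a true PFS failure in each arm when there is no treatment effect, and t = −ln(1 − q) the added hazard from the operations. The apparent HR is (h + t_d)/(h + t_l), where t_d is for degarelix and t_l for leuprolide. With p = 10% and q = 1% in both arms, this is (0.1054 + 0.0101)/(0.1054 + 0.0101) = 1.00. If a true difference exists, adding the same t to both arms pulls the ratio toward 1. Equal misclassification therefore adds noise and dilutes a real effect, but creates no false one.

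**The case against.** The best defence is that the restriction stands in the governing text. Appendix 3 can be read as a coding aid to SAP 9.3.6, and a careful programmer would apply the parent sentence. That is possible, but the SAP does not say so, and Appendix 3 presents its terms as the ones to be used. Its warning that the drug code list may be incomplete allows additions, not the removal of a listed code.

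A second objection is that the missing condition is not peculiar to one term. Table 8 lists radiation, and inclusion criteria 4C and 4E admit patients with planned radiotherapy. That is fair, but it is a different question: such radiation is related to prostate cancer, so a relatedness condition would not change how it is scored. Transurethral prostatectomy is where code and definition part on purpose.

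Third, a filter by recorded reason relies on staff who know the treatment. Arm-masked review cannot undo bias already in the recorded reason, and a fixed list is less exposed to it. This stands, and is why the unfiltered analysis should be kept alongside.

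A reader might also infer a bias toward degarelix, because Protocol 1.3 says that agonist flare may lead to "exacerbation of clinical complications such as bladder outlet obstructions, spinal cord compression, and bone pain (clinical flare"), while degarelix avoids flare. The documents do not support that step. Protocol 1.3 attributes flare to stimulation of the cancer in advanced disease, so surgery for that obstruction may properly count as related to prostate cancer. The clearly misclassified operations are those for non-cancer obstruction, and nothing suggests that these differ by arm. Anti-androgen flare protection is also allowed in metastatic patients. Putting unequal rates into the formula above does move a null HR: 0.5% against 1.5% gives (0.1054 + 0.0050)/(0.1054 + 0.0151) = 0.92 at p = 10%. But the inequality is then an assumption, not a finding.

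**Conclusion.** The inconsistency is firm on the text: SAP 9.3.6 limits this PFS component by purpose, and the list that implements it does not. This is more than missing detail, because a literal derivation gives a definite wrong classification for a non-cancer operation.

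The size is unknown. The 3% to 23% range rests on assumed procedure and failure rates and overstates the net effect for the reasons given in the working. It should not be read as an estimate, nor should the point be read as evidence of bias between arms.

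The reach is limited. PFS is one of the other secondary endpoints, analyzed without multiplicity control (SAP 9.3). The primary MACE analysis is unaffected, because the prohibited-therapy lists in Appendix 4 that trigger censoring do not include this procedure. It is a minor point that is worth correcting because the correction is simple.

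**What to change.** - State in Appendix 3 that a Table 9 procedure counts as a PFS failure only when its recorded reason is related to prostate cancer: its treatment or its progression, including tumour-related obstruction. This matches SAP 9.3.6. Limiting it to progression alone would be narrower than the endpoint and would drop qualifying therapy.
- Have unclear or missing reasons reviewed without sight of treatment arm before database lock.
- List the excluded procedures by arm, so that any imbalance can be seen.
- Report PFS with the unfiltered Table 9 list as a sensitivity analysis.

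The cost is one condition in the derivation, one listing, one repeated analysis and a read of what should be a few records. The main downside is reliance on a reason recorded by open-label sites, which Protocol 4.3.1 requires explicitly only at Screening. The unfiltered sensitivity analysis shows how much the result depends on it.
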